### Progression procedures and rules:

SARs: If 1 subject at a dose level experiences an SAE that is decided after breaking the code to be an SAR, further entry into that dose level will be at least temporarily stopped. Further accrual to that dose level may carefully proceed with more frequent adverse event monitoring and reporting. The timing of additional AE monitoring will depend on the time the SAR occurred. The additional event data, whether adverse or not, will be reported and considered by the PI and representative of the Sponsor within 7 days, with an SAE reported within 3 days. If a 2nd subject experiences an SAR, accrual to that dose level will stop and accrual to the study will stop. If not more than 1 of the 6 Biopin subjects at that dose-level experience an SAR, 8 further subjects (randomized 6 Biopin vs 2 placebo) will be entered into that dose level. Progression to the next dose-level will occur if none of the extra 6 Biopin subjects experience an SAR or a grade 4 AR.

Grade 3-4 Adverse Reactions: If  $\geq 1$  of the 6 BIOTIN 6 subjects at a dose level experiences a grade 3-4 adverse event evaluated in accordance with the National Cancer Institute Common Toxicity Criteria (NCI-CTC) (Ver 5.0) that is decided after breaking the code to be an adverse reaction, escalation to the next level of drug will be at least temporarily stopped. Progression to the next dose level will not occur unless 8 more subjects (randomized 6 Biopin vs 2 placebo) have been entered into the present dose level without any grade 3-4 adverse reactions.

Grade 2 Adverse Reactions: If  $\geq 3$  of the 6 BIOPIN 6 subjects at a dose level experience a grade 2 adverse event determined after breaking the code to be an adverse reaction, escalation to the next level of drug will be at least temporarily stopped. Progression to the next dose level will not occur unless more subjects have been entered into the present dose level with no more than one grade 2 adverse reactions.

If 0-2 of the subjects at a dose level experiences a grade 2 adverse event, escalation to the next dose level will proceed.

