## 7.8 Progression of cohorts

7.8.1 Safety considerations: Progression of dose levels (entrance of a new cohort at the next higher dose level) will depend on review of the safety data **at least through week 4** of the prior dose level.

The primary basis on which drug escalation would be limited is based on adverse reactions (an adverse event at least possibly attributable to drug). The committee that evaluates the adverse events for their relationship to drug and implements the progression rules will consist of the PI and a representative of the Sponsor, with the assistance of the Clinical Monitor and the study statistician. Before the blind is broken, the Committee will determine the grade of an AE and whether the AE is not-likely/unlikely related to implantation (ie, there is likely an alternate etiology for the event).

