#### 10.5 Relationship to investigational product

The investigator must assign a relationship of each AE to the receipt of the investigational product. The investigator will use clinical judgment in conjunction with the assessment of a plausible biologic mechanism, a temporal relationship between the onset of the event in relation to receipt of the investigational product, and identification of possible alternate etiologies including underlying disease, concurrent illness or concomitant medications. The following guidelines should be used by investigators to assess the relationship of an AE to study product administration. A physician and/or licensed practitioner (eg. NP, PA) are able to make this determination.

**Not related:** No relationship to investigational product. Applies to those events for which evidence exists that there is an alternate etiology.

**Unlikely related:** Likely unrelated to the investigational product. Likely to be related to factors other than investigational product, but cannot be ruled out with certainty.

**Possibly related:** An association between the event and the administration of investigational product cannot be ruled out. There is a reasonable temporal association, but there may also be an alternative etiology such as the subject's clinical status or underlying factors including other therapy.

**Related:** An association exists between the receipt of investigational product and the event. An association to other factors has been ruled out.

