## 10.6 Severity Assessment

All AEs will be assessed for severity by the investigator. Inherent in this assessment is the medical and clinical consideration of all information surrounding the event including any medical intervention required. Each event will be assigned one of the following categories: mild, moderate, severe, or life-threatening. Clinically Significant labs should be reported as AEs. Abnormalities in vital signs will be reviewed by the Investigator staff. The Investigator will have the authority to determine if any action needs to be taken with the abnormal vital signs and/or if the abnormality should be considered an AE. All laboratory abnormalities and vital sign abnormalities graded in accordance with CTC AE criteria will be considered when implementing progression rules (Section 7.8.1).

Any grade 4 (life-threatening) AE must be reported as an SAE.

The eCRF for AEs will reflect only the highest severity for continuous days an event occurred.

Mild	Grade 1	Does not interfere with routine activities Minimal level of discomfort
Moderate	Grade 2	Interferes with routine activities Moderate level of discomfort
Severe	Grade 3	Unable to perform routine activities Significant level of discomfort
Potentially life-threatening	Grade 4	Hospitalization or ER visit for potentially life-threatening event

FDA guidelines for toxicity will be followed; however, if a subject is evaluated in an emergency room for nonlife threatening illness or symptoms (ie, visits emergency department on weekend for mild problems because the physician's office is closed), the information from that visit will be reviewed and severity of the adverse event will be assessed according to the subject's clinical signs and symptoms.

As defined by the ICH guideline for GCP, the term "severe" is often used to describe intensity (severity) of a specific event (as in mild, moderate, or severe myocardial infarction); the event itself however, may be of relatively minor medical significance (such as severe headache). This is **not** the same as "serious", which is based on subject/event outcome or action criteria usually associated with events that pose a threat to a subject's life or functioning. Seriousness (not severity) serves as a guide for defining regulatory reporting obligations.

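### The progression rules settle whether an event is a reaction to drug after the code is broken, and the blinded screen before it asks about implantation, not drug

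*Protocol*

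**What the plan says.** Protocol 7.8.1 assigns the dose decision to a small group: "The committee that evaluates the adverse events for their relationship to drug and implements the progression rules will consist of the PI" and a sponsor representative, assisted by the clinical monitor and the study statistician. It defines an adverse reaction as an event at least possibly attributable to drug. It then describes a blinded step: "Before the blind is broken, the Committee will determine the grade of an AE and whether the AE is not-likely/unlikely related to implantation".

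The rules that follow, under Progression procedures and rules, place the adverse-reaction decision after unblinding:

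- Serious events: a subject "experiences an SAE that is decided after breaking the code to be an SAR".
- Grade 3-4, at 1 or more of 6 BIOPIN subjects: an event "that is decided after breaking the code to be an adverse reaction".
- Grade 2, at 3 or more of 6 BIOPIN subjects: a "grade 2 adverse event determined after breaking the code to be an adverse reaction".

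Separately, Protocol 10.5 says "The investigator must assign a relationship of each AE to the receipt of the investigational product", and 10.6 says "All AEs will be assessed for severity by the investigator". Protocol 10.5 also allows other qualified clinicians to make the relationship call.

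On timing, 7.8.1 sets week 4 as the minimum for safety review, 7.8.2 includes AUC to weeks 4, 8 and 12, and SAP section 11 supplies tables to a Safety Monitoring Committee once a cohort is complete.

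**The concern.** A blinded causality call protects a dose-escalation count from knowledge of the arm. With the code open, a placebo subject's event can hardly be called a reaction to drug, while the same event in a BIOPIN subject can be argued either way. That argument decides whether escalation pauses, and for grade 3-4 a single event is enough.

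The plan has a blinded step, but its question differs from the one the rules need. The documents also do not say whose code is broken (one subject's or the cohort's), who breaks it, or whether those who rate later events stay blinded. The per-subject AUCs in 7.8.2 are a second route to the same knowledge: the placebo implant contains no naltrexone (Protocol 5.2), so individual values would reveal the arm to anyone who sees them.

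**Working it through.** The plan gives no operating characteristics for the progression rules, so there is no figure to reproduce. The check has three parts.

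**1. Does the blinded step settle attribution to drug?**

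- Blinded question (7.8.1): is the event unlikely to be related to implantation?
- Question for the rules (7.8.1 definition; 5.3): is it a reaction to drug?
- Question for the individual AE record (10.5): is it related to the investigational product?

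Placebo is the same polymer implant without naltrexone (5.2). Protocol 4.4 lists procedure risks such as wound infection, bleeding and dehiscence, and local reactions to the excipients. Such an event can occur in either arm and would pass the blinded screen as related to implantation. Whether it is also a reaction to drug is still open when the code is broken.

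**2. How far can that call move the rules?**

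Let r be the probability that a BIOPIN subject has an event of the stated grade, q the share of such events attributed to drug, and p = r × q. Subjects are taken as independent. Both r and q are assumptions; the documents give neither.

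- Grade 2: P(≥3 of 6) = Σ C(6,j) p^j (1−p)^(6−j), j = 3 to 6. With r = 0.5 and q = 1: (20 + 15 + 6 + 1)/64 = 42/64 = 0.656.
- Grade 3-4: P(≥1 of 6) = 1 − (1−p)^6. With r = 0.10 and q = 1: 1 − 0.90^6 = 0.469.

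| Rule | r | q = 1 | q = 0.75 | q = 0.5 |
|---|---|---|---|---|
| Grade 2, ≥3/6 | 0.30 | 0.256 | 0.132 | 0.047 |
| Grade 2, ≥3/6 | 0.50 | 0.656 | 0.404 | 0.169 |
| Grade 2, ≥3/6 | 0.70 | 0.930 | 0.702 | 0.353 |
| Grade 3-4, ≥1/6 | 0.05 | 0.265 | 0.205 | 0.141 |
| Grade 3-4, ≥1/6 | 0.10 | 0.469 | 0.374 | 0.265 |
| Grade 3-4, ≥1/6 | 0.20 | 0.738 | 0.623 | 0.469 |

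This shows how sensitive the rules are to attribution. It does not estimate a bias that occurred.

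**3. How many later assessments could be exposed?**

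The counts are of scheduled post-dose assessments in the Protocol Timetable (2.2). They suppose that a whole cohort is unblinded straight after week 4.

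| Assessment | Total | After week 4 | Share |
|---|---|---|---|
| AE checks (8, 24, 48, 72 h; weeks 1-12) | 16 | 8 | 50% |
| Vital signs (week 12 before and after explant) | 18 | 9 | 50% |
| Chemistry and hematology | 4 | 2 | 50% |
| C-SSRS | 3 | 2 | 67% |
| HAM-D | 6 | 4 | 67% |
| ECG (week 12 before and after explant) | 4 | 3 | 75% |

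By time, 8 of 12 implant weeks (67%) would follow. If review instead waits for week 12 PK (7.8.2) or cohort completion (SAP section 11), at most the post-explant vital signs and ECG and the week 14 visit remain.

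**The case against.** The strongest reply is that the step after unblinding is mechanical. Grade is fixed while blinded. An event not screened out as unlikely is at least possibly related, which matches the 7.8.1 definition of an adverse reaction, so opening the code only shows whether the subject had active drug. This reading is plausible, and the protection of grade stands. The text does not secure the rest. The rules speak of deciding or determining a reaction after the code is broken, and the blinded screen concerns implantation. A purely mechanical step would count every implantation-related complication in a BIOPIN subject as a reaction to drug, and nothing says that this is intended.

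Several stronger conclusions are tempting, but the documents do not support them:

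- A reader might infer that the code is broken at every dose review. The rules mention it only for qualifying events.
- A reader might infer that most later safety assessments are unblinded. That needs whole-cohort unblinding at about week 4, and even then it is half of the AE, vital-sign and laboratory assessments.
- A reader might infer that the PI attributes every event. Protocol 10.5 allows others to do so.
- A reader might infer that the related columns of SAP Tables 12 and 14-16 carry the committee's unblinded decisions. No text says that these overwrite the relationship on the eCRF, and Tables 13, 17 and 18 do not use attribution.
- A reader might infer that PK review unblinds the PI. Protocol 7.8.2 compares group means and does not say who sees individual values.

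It is also fair that the study is called placebo-controlled, never double-blind, although 7.8.1 presupposes a blind.

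**Conclusion.** The point holds in a limited form. As written, the attribution that feeds the escalation counts can be made with the arm known, by a committee that includes the PI, and the blinded step does not close that gap. The grade 3-4 rule can turn on one subject in six. Under the assumed rates, moving from full to half attribution changes the chance of triggering from 0.656 to 0.169 (grade 2, 50% event rate) and from 0.469 to 0.265 (grade 3-4, 10% event rate). Exposure of later assessments ranges from roughly half or more of a cohort's schedule to almost none, depending on scope and timing that the documents leave open or state inconsistently.

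The consequence is confined to escalation and AE attribution. PK is primary, SAP section 7 tests no hypothesis, and SAP section 3 attributes the stop after dose level 2 to exposure, not to a safety rule. Nothing shows that any actual decision was distorted. This is a cheap improvement worth making, not a threat to the main result.

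**What to change.** Keep all thresholds and visits as they are.

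- In Protocol 7.8.1, reconcile the relationship question between the blinded step and the three rules. Make the committee's blinded classification of grade and relationship final for those rules, so that breaking the code only assigns each classified event to BIOPIN or placebo.
- Have the study statistician, who already assists the committee, hold the code and the individual PK results, and return BIOPIN counts and group mean AUC and Cmax.
- Keep AE assessors blinded to individual assignment except where a subject's safety requires unblinding. State whose code may be broken, and by whom.
- Reconcile the review timing in 7.8.1, 7.8.2 and SAP section 11, and the 7.8.1 committee with the SAP's Safety Monitoring Committee.
- For cohorts already run, report who was unblinded, when, and whether attribution came first. Because SAP section 3 records that escalation ended after dose level 2, this is the part that still bears on the present results; the rule wording matters for any further escalation.

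The cost is revised wording and a short unblinding procedure, with no new staff or visits. The PI would see counts rather than subject-level assignments, and a count of one may still identify the affected subject.

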### 7.8.2 Pharmacokinetic considerations

Progression of dose levels (entrance of a new cohort at the next higher dose level) will also depend on review of the naltrexone PK data of the prior dose level. AUC (0-T) will be calculated for T=4 weeks, T= 8 weeks, and T=12 weeks for each subject, statistically summarized for the group, and the mean values will be compared to the reference values for the most sensitive animal species (dog) for which AUC was 3,267 ng/ml x hr up to 4 weeks, 6,117 ng/ml x hr up to

8 weeks, and 13.239 ng/ml x hr up to 12 weeks. In addition, the mean Cmax for dog for which the reference value was 42 ng/ml. If the mean clinical Biopin AUC or Cmax values exceed any of these reference values by 31%, the new cohort will not be entered until further consultation with the FDA.

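### Protocol 7.8.1 clears the same 6+2 expansion by two different tests without saying that both apply, and the test after an SAR lets non-serious grade 3 reactions through

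*Protocol*

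**What the plan says.** Protocol 7.8.1 has separate paragraphs for SARs, for grade 3-4 ARs and for grade 2 ARs.

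- **SAR paragraph.** After one SAR, "further entry into that dose level will be at least temporarily stopped". Accrual may then resume: "Further accrual to that dose level may carefully proceed with more frequent adverse event monitoring and reporting". If no more than one of the 6 Biopin subjects has an SAR, "8 further subjects (randomized 6 Biopin vs 2 placebo) will be entered into that dose level". The clearance test is: "Progression to the next dose-level will occur if none of the extra 6 Biopin subjects experience an SAR or a grade 4 AR". At a second SAR, "accrual to that dose level will stop and accrual to the study will stop".
- **Grade 3-4 paragraph.** The trigger is one or more "of the 6 BIOTIN 6 subjects at a dose level experiences a grade 3-4 adverse event" (the product name is misspelt there) judged after unblinding to be an AR. Progression is barred unless 8 more subjects, in the same 6 to 2 split, "have been entered into the present dose level without any grade 3-4 adverse reactions".

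Three other places matter. Section 5.3, a brief summary, makes entry of cohorts 2 and 3 depend on the preceding cohort showing no grade 3-4 adverse reaction. Section 7.8.2 adds the pharmacokinetic gate expressly: progression "will also depend on review of the naltrexone PK data of the prior dose level". Section 10.6 requires every grade 4 AE to be reported as an SAE, keeps severity apart from seriousness, and counts CTC-graded laboratory and vital-sign abnormalities when the progression rules are applied.

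**The concern.** The two paragraphs call for the same expansion but judge it differently, and no sentence in 5.3, 7.8.1, 7.9, 10.6 or the SAP says which test governs or that both must be met. The SAR sentence is worded as a sufficient condition for progression, and the grade 3-4 sentence as a necessary one.

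A related grade 4 event, or a related grade 3 event that is also serious, triggers both paragraphs. If the expansion then yields one non-serious grade 3 reaction and no SAR, the first sentence, read literally, permits escalation and the second forbids it.

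An SAR below grade 3 triggers only the SAR paragraph. One non-serious grade 3 reaction among the first 6 Biopin subjects would have held escalation, yet the same reaction among the extra 6 passes. That is an odd result for a safety rule in the first human use of the implant, in healthy volunteers.

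**Working it through.** The documents give no operating characteristics for these rules, so there is no planned figure to reproduce. The check compares the texts and then sizes the gap with assumed rates.

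**Step 1. What the SAR test screens out.** By 10.6 every grade 4 AE is an SAE, so every grade 4 AR is an SAR. The words on grade 4 in the SAR test therefore add nothing, and the test reduces to no SAR among the extra 6. Grade 3 is where an added term would have effect, and it is not named.

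**Step 2. Where the tests differ.** Take the SARs in the expansion as grade 3-4.

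| Expansion of 6 Biopin subjects | SAR test | Grade 3-4 test |
|---|---|---|
| No SAR, no non-serious grade 3 AR | clears | clears |
| No SAR, at least one non-serious grade 3 AR | clears | does not clear |
| At least one SAR, with or without a non-serious grade 3 AR | does not clear | does not clear |

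They part in one row. For an SAR below grade 3 the order reverses: the SAR test fails it, and the grade 3-4 test as worded does not.

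**Step 3. Chance of disagreement, given an expansion triggered by one SAR.** Inputs: n = 6 (7.8.1). Assumed: q, the per-subject SAR rate, and p, the per-subject rate of a non-serious grade 3 AR, taken as mutually exclusive. An SAR in the expansion is a second SAR and never clears.

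- SAR test clears: (1−q)^6
- Test of no SAR and no AR of grade 3 or higher clears: (1−q−p)^6
- Disagreement D is the difference.

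| q | p | SAR test | Stricter test | D |
|---|---|---|---|---|
| 1% | 5% | 0.9415 | 0.6899 | 0.252 |
| 1% | 10% | 0.9415 | 0.4970 | 0.444 |
| 1% | 20% | 0.9415 | 0.2431 | 0.698 |
| 1% | 30% | 0.9415 | 0.1079 | 0.834 |
| 5% | 5% | 0.7351 | 0.5314 | 0.204 |
| 5% | 10% | 0.7351 | 0.3771 | 0.358 |
| 5% | 20% | 0.7351 | 0.1780 | 0.557 |
| 5% | 30% | 0.7351 | 0.0754 | 0.660 |

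**Step 4. Unconditional chance per dose level.** Exactly one SAR in the first 6 has probability 6q(1−q)^5, which is 0.0571 at q = 1% and 0.2321 at q = 5%. Let s be the assumed share of SARs graded 3-4. Both rules are triggered with probability

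6q(1−q)^5 × [s + (1−s)(1 − ((1−q−p)/(1−q))^5)].

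The second term in the bracket is a separate non-serious grade 3 AR in another first-cohort subject. With p = 10% and s = 0.5:

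- q = 1%: 0.0403 × 0.444 = 0.018
- q = 5%: 0.1656 × 0.358 = 0.059

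With s = 1, an upper bound, and p = 10%: 0.0571 × 0.444 = 0.025 and 0.2321 × 0.358 = 0.083. Over p from 5% to 30% the upper bounds run from 0.014 to 0.048 (q = 1%) and from 0.047 to 0.153 (q = 5%).

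**The case against.** The strongest reply is that only a cumulative reading makes 7.8.1 work. Its last line says that escalation proceeds when 0 to 2 subjects have a grade 2 event. Taken as self-sufficient, that line would override the SAR and grade 3-4 rules, and the SAR sentence would likewise override the pharmacokinetic gate. Each permissive sentence is better read as clearing its own rule only, so the grade 3-4 paragraph remains a veto. Section 5.3 points the same way, since any grade 3-4 reaction in the preceding cohort bars entry.

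Most of this stands for double triggers: a careful committee would probably apply both rules. Two gaps remain. Section 7.8.1 does not state the cumulative reading for its own rules, although 7.8.2 does so for the pharmacokinetic gate. And the reading does not clearly reach an SAR-only expansion, because the grade 3-4 paragraph counts reactions among the 6 subjects at a dose level and does not mention the extra 6. Section 5.3 does not close this gap. It is a summary that names neither SARs nor the expansion, and taken literally it would block escalation even after a clean expansion.

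A reader might also infer that 7.8.1 is at fault for treating a drug-related death as one SAR. The documents do not support calling that an error. Entry already stops at the first SAR, resumption is permissive, and 7.9 lets the investigator (after consulting the sponsor) or the sponsor terminate the study. A clause specific to death would be a preference.

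**Conclusion.** The point holds as a drafting inconsistency in a first-in-human safety rule. The same expansion has two clearance tests with no stated relation between them, and the SAR test omits the one grade at which an added term would matter.

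Two stronger readings should be resisted. The SAR test is not laxer on all grade 3 reactions: a serious one fails it as an SAR, and the test is stricter on SARs below grade 3. Nor does anything show that an escalation decision went wrong, because the documents do not report that an expansion was triggered.

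The size is modest and rests wholly on assumed rates. A double trigger followed by disagreement has a chance of about 2% to 6% per dose level at a 10% non-serious grade 3 rate, if half of SARs are grade 3-4 and the SAR rate is 1% to 5%. The larger figures in step 3 apply only once an expansion has been triggered by an SAR. SAP section 3 records that no dose above level 2 was pursued, so the wording bears only on the step from level 1 to level 2 and on any later study that reuses it.

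**What to change.** Two changes to Protocol 7.8.1, or to the text carried into a later protocol, with no change to the SAP:

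1. In the SAR clearance sentence, replace the reference to a grade 4 AR with an AR of grade 3 or higher.
2. Add: *All applicable rules must be met, so the stricter governs.*

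The second change alone removes the double-trigger conflict. It is enough if the sponsor wants to keep the laxer test after an SAR-only trigger as a deliberate choice.

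The first change lowers the chance of escalating after an SAR-only trigger. Given such an expansion and an assumed 10% non-serious grade 3 rate, the chance of clearing falls from 74% to 38% at a 5% SAR rate, or from 94% to 50% at 1%. For double triggers there is no cost if the rules were always meant to be cumulative.

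If an expansion did occur at level 1, the study report should state which reading was applied.
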